5 MATERIALS AND METHODS

5.1 STUDY DESIGN

5.1.1 OVERALL DESIGN

This study will be conducted at several optometry practices in the US and Canada. This study is a prospective, bilateral eye, subjected-masked, randomized, 1-month cross-over, daily-wear design involving two different silicone hydrogel toric lens types. Each lens type will be worn bilaterally for approximately one month, during which participants record their subjective lens-wear experience on three different days. Additional measures will be collected during in-office study visits.

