5.1.2 RANDOMIZATION

A randomization schedule will determine the order of Lens A and Lens B wear for the first/second month for each participant. Participants will be randomized immediately prior to their first lens dispense.

This randomization schedule will be generated for each site using a web-based program: (www.randomization.com). The lens type that will be worn during the first month is called "Lens type #1", the lens type dispended for the second month is called "Lens type #2". The final study randomization schedule will be generated by CORE's Database Administrator and provided to the research assistants at each site.

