5.3.2 NUMBER OF PARTICIPANTS

Participants will be recruited using site records and databases where consent for contact about research has been provided. There will also be general advertising materials (e.g. posters, social media posts) and all these, including email scripts, will be approved by the ethics review board. All initial individual-targeted recruitment activities, such as any direct mailing of recruitment scripts, will be conducted by practice staff that are not directly involved in conducting the research. This separation will reduce any undue influence of the optometrist-patient relationship. This process will also eliminate opportunity for the investigator to access personal health information before any consent for disclosure is provided by the potential participant.

It is anticipated that up to 60 potential participants may attend a Screening visit and at least 48 participants will be randomized and dispensed with study products, with a target of at least 44 completing the study. Each site will dispense study products to approximately 10 participants.

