5.5 SCHEDULED AND UNSCHEDULED VISITS

This study has a minimum of 4 scheduled study visits, including the screening visit. There is an option for repeated screening visit if needed.

A scheduled 1-month follow-up visit may only take place when the participant attends wearing the study lenses for at least two hours that day. If this is not the case and the participant is not experiencing any problems with the lenses, the appointment will be rescheduled, ideally within the visit window.

Visits that fall outside of the specified visit windows will be designated as protocol deviations and at the end of the study, the data collected during protocol deviations will be assessed for their suitability to be included in the analysis population.

Table 3 summarizes the scheduled study visits and study codes.

Table 2: Summary of visits

Visit code	Approximate Duration	Visit Description
0	2 hrs	Screening, Habitual baseline (collect in-office ratings for subjective experience, satisfaction and agreement questions) & Fitting of study lenses
0/R1, 0/R2	As needed	Repeat Visit 0 if needed
1-0	0.75 hr	Dispense Lens type #1 (0-28 days after Visit 0); collect in-office subjective ratings after 10 mins of lens insertion; provide at-home diaries
2-0	1.5 hr	1-month follow-up Lens type #1 (28-32 days after 1-0); review at-home diaries; collect in-office ratings for subjective experience, satisfaction and agreement questions for Lens type#1
		Dispense Lens type #2; collect in-office subjective ratings after 10 mins of lens insertion; & Provide at-home diaries
3-0 and exit	1.5 hr	1-month follow-up Lens type #2 (28-32 days after 2-0); review at-home diaries; collect in-office ratings for subjective experience, satisfaction and agreement questions for Lens type#2; collect preference ratings between Lens type#1 and Lens Type#2
		Exit forms & remuneration

Visits 1-0 (Dispense Lens type #1) and 2-0 (Dispense Lens type #2) will count as day 0 Lens type #1 and #2 will be either Lens A or B, as determined by the randomization table.

[figure not shown]

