12 STATISTICAL ANALYSIS AND DATA MANAGEMENT

12.1 STATISTICAL ANALYSIS

All data will be analyzed by CORE at the University of Waterloo. Unmasked data analysis will be conducted using Statistica 14.0, Statsoft or other suitable software. Descriptive statistics will be provided on demographic data (age, gender, refractive error distribution, etc.). Table 7 lists the primary and other outcome variables and anticipated statistical procedures.

Visual acuity results will be converted to LogMAR for analysis purposes.

Comparisons will be made between the study lenses for the variables measured at the 1-month visits. Additionally, the subjective ratings completed on days 7, 14 and 27 with each study lens will be compared. A binomial test will be used to analyze the results for the count data of subjective preferences and experience responses. Where relevant, the number of "no preference" responses will be evenly distributed to the two options on the basis they would be equally likely to choose either.

For assessments conducted for each eye separately, the right eye will be used for analysis. If a general difference is found (paired t-test / Wilcoxon matched pairs) between OD and OS, a comment will be provided.

Where appropriate, data may be presented as both mean or median and as counts by 'bucket' groups.

Additional analysis may be conducted.

Table 6: Statistical procedures

Variable	Analysis	Statistical test
	Comparison between study lenses	Freidman ANOVA
	and time points	Wilcoxon matched pairs test
	Comparison between study days	Freidman ANOVA
	and/or between contact lenses per	Wilcoxon matched pairs test
	time point.	RMANOVA
Demographics,	Descriptive stats	One or more: mean,
lens fit variables		median*, mode, standard
		deviation, minimum,
		maximum, frequency count

^{*} For non-parametric data only

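### The readable lens comparisons for this two-period crossover name no period term; prespecifying one is a cheap, optional refinement, not the repair of an error

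*Combined protocol and SAP*

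**What the plan says.** Section 5.1.1 describes a two-lens crossover: "Each lens type will be worn bilaterally for approximately one month". Section 5.1.2 randomises order only: "A randomization schedule will determine the order of Lens A and Lens B wear for the first/second month for each participant". Section 5.5 repeats this: "Lens type #1 and #2 will be either Lens A or B, as determined by the randomization table". On how the order is allocated, section 5.1.2 says "This randomization schedule will be generated for each site using a web-based program". It states no ratio or block size and rules neither out. Section 5.3.2 expects that "at least 48 participants will be randomized and dispensed with study products, with a target of at least 44 completing the study".

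For the analysis, section 12.1 says "Comparisons will be made between the study lenses for the variables measured at the 1-month visits". One comparative row of Table 6 begins "Comparison between study lenses" and goes on to time points. The tests listed across the two comparative rows are Friedman ANOVA, "Wilcoxon matched pairs test" and, in the row on study days, RMANOVA. No factors are given for RMANOVA. The variable cells of both rows are unreadable in the public copy, so the test for the primary outcome (ease of removal at the 1-month visits, section 3) cannot be identified. Time points are not defined as the crossover months, and section 12.1 separately plans comparisons of the ratings on days 7, 14 and 27. The section also leaves room for further analyses without naming any.

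**The concern.** In a crossover each participant's A minus B difference mixes the lens effect with any general change between the two months. If ratings move by π points from month 1 to month 2 whatever the lens, a participant who wears A first contributes the lens effect minus π, and one who wears B first contributes the lens effect plus π. A paired test that ignores order treats that ±π as random noise when the sequences are equal in size. When they are unequal, part of it stays in the lens estimate as bias.

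At stake are some power for the primary comparison and, in a trial whose completers happen to split unevenly, a displaced estimate and a type I error, given that split, that is not 5%. Naming the model in advance also removes a later choice between adjusted and unadjusted results, which matters a little more because section 12.1 says the analysis is unmasked.

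**Working it through.** **Inputs from the documents.** 44 completers, 90% power and SD 20 on the 0–100 scale (section 5.3.1). Section 5.3.1 does not say whether the SD is for one rating or for the paired difference.

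**Assumptions, not in the documents.** Two-sided 5%; lens effect τ = 10 points; SD of paired differences σ = 20; period shift π (month 2 minus month 1) examined from 0 to 10 points.

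**Reproducing the plan's figure.** A paired t-test with τ = 10, σ = 20 and two-sided 5% needs N = 44 and has power 90.0%. The match depends on the assumed effect and alpha.

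**Formulas.** With nAB and nBA completers per sequence and N = 44:
- Unadjusted estimate: mean τ + π(nBA − nAB)/N, 43 df. Its sum of squares divided by σ² is noncentral chi-square with noncentrality 4·nAB·nBA·π²/(Nσ²).
- Adjusted estimate: average of the two sequence means, unbiased for τ, 42 df, SE = (σ/2)·√(1/nAB + 1/nBA).

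**Noise, equal sequences (22/22).** The noncentrality is 44 × 25/400 = 2.75 at a 5-point shift and 44 × 100/400 = 11 at 10 points. The error SD used by the unadjusted test therefore rises from 20 to √(400 × 45.75/43) = 20.6 and √(400 × 54/43) = 22.4.

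| Shift, 22/22 | Unadjusted power | Adjusted power |
|---|---|---|
| 0 | 90.00% | 89.97% |
| 3 | 89.6% | 89.97% |
| 5 | 88.9% | 89.97% |
| 10 | 85.1% | 89.97% |

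**Bias, unequal sequences, 5-point shift.** The size of the bias is π × |nAB − nBA|/N. Its direction depends on the sign of the shift and on which sequence is larger.

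| Split | Bias (points) | Unadjusted power, bias opposing / adding | Adjusted power |
|---|---|---|---|
| 24/20 | 5 × 4/44 = 0.45 | 86% / 91% | 90% |
| 26/18 | 5 × 8/44 = 0.91 | 82% / 93–94% | 89% |
| 28/16 | 5 × 12/44 = 1.36 | 78% / 95% | 88% |

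The higher figure in each pair reflects an overstated lens effect, not a real gain.

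**Type I error given the split, 10-point shift.** Unadjusted: about 2.9% at 22/22 (conservative) and about 10% at 28/16. Adjusted: near 5% at both.

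**Cost with no shift.** The adjusted SE is 3.015 at 22/22, 3.066 at 26/18 and 3.134 at 28/16, against 20/√44 = 3.015 unadjusted. Adjusted power is 89.97%, 89.0% and 87.6%, against 90.0%. The cost is 0.03, about 1 and about 2 points. For the rank version it is under half a point, about 2 and about 3 points.

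**Break-even on mean squared error, unequal splits.** Setting squared bias equal to the extra variance gives π = σ·√(N/(4·nAB·nBA)) = 10·√(44/(nAB·nBA)): 3.03 at 24/20, 3.07 at 26/18 and 3.13 at 28/16, close to σ/√N = 3.02.

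If SD 20 is for a single rating with within-person correlation ρ, then σ = 20·√(2(1 − ρ)) and σ/√44 is:
- ρ = 0: 28.28/√44 = 4.3 points
- ρ = 0.5: 20/√44 = 3.0 points
- ρ = 0.8: 12.65/√44 = 1.9 points

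**Break-even on power** (σ = 20) is lower: 0.84 points at 22/22, and 0.70 at 25/19 when the bias opposes the lens effect.

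**The case against.** The strongest reply is that nothing here is wrong. Paired tests are valid when order is randomised, and averaged over unrestricted allocation the unadjusted analysis is unbiased with type I error of about 5%. Every participant already wears soft toric lenses (section 5.3.3) and rates a typical day in the past month (section 3), so the documents give no reason to expect a large shift. Marked imbalance may also be unlikely. A split of 26/18 or worse has a 29% chance under unrestricted allocation of 44, but only about 1.5% if each site's schedule used blocks of 4 (assuming 48 randomised and 4 random dropouts). Section 5.1.2 does not say which applies. All of this stands, and it is why the point is minor.

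It is also fair that RMANOVA might include period and that the unreadable cells might say more. A reader might infer that the plan has no period adjustment at all. The documents do not support that: they show only that none is visible. The opening for additional analyses permits an adjusted analysis but does not prespecify one.

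A reader might also infer that adjustment pays off only if ratings shift by more than about 3 points. That is too strong. Three points is the mean-squared-error break-even for unequal splits at an assumed SD of differences of 20; on power, the gain at 22/22 starts at about 0.8 points. It is simply negligible below about 3 points near balance.

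**Conclusion.** The point holds as an optional improvement. No period term is visible in the readable lens comparisons, and the listed matched-pairs and Friedman tests cannot carry one. Near balance, adjustment costs almost nothing. Its benefit is negligible for small shifts and grows with the shift and with imbalance. With unequal sequences the benefit is removal of bias and a type I error, given the split, near 5%; it is not a narrower interval. At 28/16 with a 5-point shift the mean 95% CI half-width is 6.29 adjusted against 6.22 unadjusted.

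The figures rest on an assumed 10-point effect, SD of differences 20, two-sided 5% and t-type analyses. The break-even moves between about 4.3 and 1.9 points if SD 20 is for a single rating (correlation 0 to 0.8). Since the documents give neither a size nor a direction for any period shift, a stronger reading, that the planned comparison is invalid or biased, is not supported.

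**What to change.** In section 12.1 and Table 6, prespecify the primary 1-month ease-of-removal comparison as a mixed model with fixed lens and period and random participant. A sequence term is optional and no carryover test is needed. If a rank method is kept, use a Wilcoxon rank-sum test of the month-1 minus month-2 differences between the two sequences. State the RMANOVA factors. The lens comparisons on days 7, 14 and 27 may be handled the same way.

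The cost is wording plus one degree of freedom. Period is known from the randomisation schedule, so no new data or participants are needed. The price is the small no-shift power loss shown above and a slightly wider interval if the sequences end up markedly unequal.

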3 OBJECTIVES

To compare the clinical performance of Biofinity toric versus Total 30 for astigmatism in habitual lens wearers, when worn for 1-month each.

The primary outcome variable:

• Ease of handling for lens removal (0 - 100) reflecting a typical day in the past month, collected at the 1-month in-office visits

The secondary outcome variable:

Distance Visual Acuity (Snellen converted to logMAR) for study lenses determined at the
 1-month in-office visits

Other outcome variables:

- o Lens fit: centration, lens orientation, post blink movement at 1-month follow-up
- Subjective ratings:
 - At-home questionnaires [collected on Days 7, 14 and 27 (study CL)]
 - In-office experience ratings after lens insertion [collected at lens dispense visit (study CL)]
 - In-office experience ratings a typical day in the past week [collected at screening (habitual CL) and 1-month follow-up visits (study CL)]
 - In-office satisfaction ratings a typical day in the past week [collected at screening (habitual CL) and 1-month follow-up visits (study CL)]
 - In-office agreement ratings— a typical day in the past week [collected at screening (habitual CL) and 1-month follow-up visits (study CL)]
 - In-office preference ratings collected at exit visit (study CL)

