5.3 STUDY POPULATION

5.3.1 SAMPLE SIZE CALCULATION

The sample size calculation was based on a recent study comparing Biofinity sphere and Total30 sphere; the data for subjective responses for ease lens handling for lens removal when reflecting in a typical day, collected at the 1-month visits: standard deviation of 2.0 (0 - 10 scale) was transformed to a standard deviation of 20 for using a 0 - 100 scale for this study. 90% power is achieved with a minimum sample size of 44 participants.

Therefore, up to 48 participants will be dispensed with study products with the goal to complete at least 44.

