10 DEVICE MALFUNCTIONS

A device malfunction means the failure of the device to meet its performance specification or otherwise perform as intended. Any defective lens that is *likely* to cause or contribute to a *Serious Adverse Event* should be reported to CORE and the sponsor **within 24 hours** of the investigator becoming aware of the malfunction. Sterling IRB would also be notified within 24 hours of any device malfunction that may contribute to a *Serious Adverse Event*.

Other defective lenses should be reported to CORE as soon as possible.

This clinical study will also ascertain satisfaction or preference with subjective attributes such as comfort, vision, or lens handling. Responses to these subjective questionnaires will not be considered as complaints or device malfunctions.

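### Splitting no-preference answers evenly and then applying a binomial test overstates the null variance and leaves odd counts without a rule

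*Combined protocol and SAP*

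**What the plan says.** Section 12.1 states: "A binomial test will be used to analyze the results for the count data of subjective preferences and experience responses". It then says that, where relevant, no-preference "responses will be evenly distributed to the two options on the basis they would be equally likely to choose either". It does not state the denominator of the test, the significance level or sidedness, an expected no-preference rate, or what to do when the number of such answers is odd. It describes the analysis as unmasked.

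Preference is listed among the other outcome variables in section 3: "In-office preference ratings collected at exit visit (study CL)". Table 2 in section 5.5 places it at the final visit: "collect preference ratings between Lens type#1 and Lens Type#2". Section 10 gives an idea of the attributes: "This clinical study will also ascertain satisfaction or preference with subjective attributes such as comfort, vision, or lens handling". Which of these carry a preference question cannot be seen in the public text.

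The number of participants comes from section 5.3.1: "up to 48 participants will be dispensed with study products with the goal to complete at least 44".

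**The concern.** The plan's justification does not support its rule. If undecided participants really were equally likely to choose either lens, T forced choices would vary as Binomial(T, 0.5). An exact even split removes that variation, but a binomial test on all N still allows for it. The test is then generally too conservative, increasingly so as no-preference answers become common, and a real preference is more likely to be missed.

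Separately, an odd T cannot be split evenly in whole answers. Someone has to decide where the last one goes, and with 44 to 48 participants a single answer can carry the p-value across 0.05. Since the analysis is unmasked, that choice should be fixed beforehand.

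**Working it through.** **Inputs.** N = 44 to 48 (section 5.3.1). The documents give no design figure for the preference test, so there is none to reproduce; the 44 was set for the primary handling rating. Assumed, because the documents do not state them: two-sided 5%, a null of 50:50, no-preference rates t from 0 to 50%, and a true 70:30 preference among those who choose.

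**Variance.** Let A and B be the expressed preferences and T the undecided, with A + B + T = N. After the split the count for the first lens is A + T/2. Given T, its null variance is that of A alone, (N-T)/4. Binomial(N, 0.5) assumes N/4. With T = tN the overstatement is 1/(1-t): 1.25 at 20%, 1.43 at 30%, 2 at 50%. In z terms,

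- rule: z = (A-B)/√N
- expressed preferences only: z = (A-B)/√(N-T)

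so the rule shrinks z by √(1-T/N).

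**Examples with even T (exact two-sided p).**

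- 21 v 9, 14 undecided, N=44. Rule: 28 of 44, p = 0.096. Expressed only: 21 of 30, p = 0.043. (z = 12/√44 = 1.81 against 12/√30 = 2.19.)
- 27 v 13, 8 undecided, N=48. Rule: 31 of 48, p = 0.060. Expressed only: 27 of 40, p = 0.038.

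Over every outcome with even T at N=44 to 48, the rule's p-value is never below the expressed-only value.

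**Operating characteristics.** Exact enumeration with T ~ Bin(N, t) and A given T ~ Bin(N-T, θ), rejecting at p ≤ 0.05. N=44, odd leftover placed at random:

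| No-preference rate | Type I error, rule | Type I error, expressed only | Power at 70:30, rule | Power at 70:30, expressed only |
|---|---|---|---|---|
| 5% | 4.4% | 3.6% | 74% | 71% |
| 10% | 3.9% | 3.4% | 69% | 67.5% |
| 20% | 2.8% | 3.3% | 58% | 61% |
| 30% | 1.9% | 3.1% | 45% | 54% |
| 50% | 0.6% | 2.9% | 18% | 39% |

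The two methods are about equal at 15%. At N=48 the power is 65/53/39/13% under the rule against 73/66/59/42% at rates of 10/20/30/50%.

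**Discreteness.** The gap depends on N because the exact full-N test with no undecided answers has a size of 4.9% at N=44 but 2.6% at N=46. N=44 therefore understates the effect of the rule itself and N=46 overstates it. A normal approximation, free of this, gives losses of about 2/4/9/16/30 points at 5/10/20/30/50%, nearly the same at N=44 and N=48.

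**Odd T.** With 28 v 15 and 1 undecided (N=44), p is 0.066 among expressed preferences (28 of 43), 0.049 if the leftover goes to the leading lens (29 of 44) and 0.096 if it goes to the other (28 of 44). Compared with the expressed-only test, giving the leftover to the leader creates significance in four configurations:

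- N=44: 28 v 15 + 1, 27 v 14 + 3, 26 v 13 + 5
- N=47: 30 v 16 + 1

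Always favouring the leader at N=44 gives a type I error of 5.25% at a 5% rate (peak 5.5% at 2%), and power of 62/49/21% at 20/30/50%. Favouring the trailing lens, or dropping the leftover, gives 3.6% at the 5% rate and power of 55/42/15%.

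**The case against.** The best defence is that this is loss of efficiency on a minor outcome, and that its size cannot be known. The split applies only where relevant. The denominator N is inferred. The no-preference rate, true split, level and sidedness are all assumed, and the questionnaire is not visible. The rule is mostly conservative, so it makes a false claim of preference less likely. It also keeps every participant in the summary. At N=44 with 10% or fewer undecided answers, it is slightly more powerful than the alternative when the leftover is placed at random. Placement of the leftover seldom decides the result: at N=44 and rates of 5 to 30%, in about 0.9 to 1.6% of trials under the null and 5 to 8% under 70:30. A one-line convention would close that gap. The plan also leaves room for additional analyses.

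Most of this stands as a limit on weight. The threshold of roughly 20 to 30% belongs to N=44; at N=46 and N=48 some loss already appears at 5%. Nothing in the conduct of the trial suggests that the leftover would be misused. But the qualifier does not say when the split applies, no reading of the text restores the missing variation if all N are tested, and an open-ended permission for further analyses is not a pre-specified test. The sentence that "data may be presented as both mean or median and as counts by" bucket groups allows counts to be shown but does not require the three preference counts, and it reads more naturally as being about rating scales.

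**Conclusion.** The concern holds, at minor-to-moderate weight. Tested on all N, evenly split answers give p-values based on a null variance too large by 1/(1-t), and the missing odd-count rule can by itself decide significance. At a two-sided 5% level and a true 70:30 preference, the change in power (rule minus expressed-only), over N=44 to 48 and all four ways of handling the leftover (random, leader, trailer, dropped), is:

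- +5 to -10 points at a 5% no-preference rate
- +5 to -13 at 10%
- +0.4 to -19 at 20%
- -5 to -25 at 30%
- -18 to -32 at 50%

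The worst values come from N=46 and partly reflect discreteness. Type I error exceeds 5% only at N=44, with the leftover always given to the leader and a rate below about 8%. The arithmetic is firm; the practical impact depends on a no-preference rate that the documents do not give. The primary and secondary outcomes and the sample size are unaffected.

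**What to change.** Replace the allocation sentence in section 12.1 with: 'The exact binomial (sign) test is run on participants who express a preference; the counts and percentages preferring A, preferring B and with no preference are all reported.' A plus half of the no-preference answers may be kept as a labelled descriptive summary of all participants, but should not be tested with n = N. This also removes the odd-count gap.

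The cost is one sentence and no new data. Each test has a smaller n. The inference applies to those who express a preference, so the no-preference percentage must stand beside it. At N=44 with 10% or fewer undecided answers, the replacement gives up about 2 to 3 points of power against the split with a random leftover.
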